6.4 Treatment blinding

This is a patient and investigator-blinded study. Patients and investigators will remain blinded to study treatment throughout the blinded treatment phase of the study, except where indicated below.

Patients, investigator staff, persons performing the assessments, and the clinical trial team (CTT) will remain blind to the identity of the treatment from the time of randomization until end of the Week 29 visit applying the following rules:

- Randomization data are kept strictly confidential until the time of unblinding,
- Unblinding will occur in the case of subject emergencies and at the conclusion of the study.
- Unblinding of the CTT members may occur at the time of the interim analyses.

Site staff

With the exception of any unblinded site staff identified below, all site staff (including study investigator and study nurse) will be blinded to study treatment throughout the blinded treatment phase of the study.

Unblinding a single patient at site for safety reasons (necessary for subject management) will occur via an emergency system (IRT) in place at the site.

Drug product will be supplied in open label medication packs; therefore, an unblinded pharmacist who is independent of the study team will be required in order to maintain the blind. The unblinded pharmacist will receive the appropriate treatment allocation numbers via the IRT system. Appropriate measures must be taken by the unblinded pharmacist to ensure that the treatment assignments are concealed from the rest of the site staff.

Sponsor staff or delegate

The following unblinded sponsor roles are required for this study:

The randomization codes associated with subjects from whom PK samples are taken will be disclosed to PK analysts who will keep PK results confidential until data base lock.

- Unblinded sample analysts CCI [REDACTED]

CCI [REDACTED]

- Unblinded Clinical Trial Associate role to have oversight of randomization in IRT system
- Unblinded field monitors

The unblinded field monitors are required to review drug accountability and allocation at site. The unblinded monitors are not provided with a randomization list directly but will be unblinded through review of source documentation compiled by the unblinded pharmacist, which details treatment allocation to individual subjects. The unblinded monitors will also be able to review the randomization list provided to the unblinded pharmacist.

The sample analysts will receive a copy of the randomization schedule (via request to the Randomization Office), to facilitate analysis of the samples. The sample analysts will provide the sample data to the study team under blinded conditions unless otherwise allowed.

The study statistician will be able to access the randomization list for interim analyses and is allowed to share unblinded information with the rest of the clinical team as appropriate for internal decision purposes, as outlined in [Table 6-4](#). For example, unblinded summaries and unblinded individual data can be shared with the team for interim analyses.

Study programmers and other personnel involved in study data analysis CCI [REDACTED] are allowed to access treatment assignment information for the purpose of conducting interim analyses.

The clinical trial team is allowed to share unblinded results with other sponsor staff (e.g., decision boards) as required for internal decision making on the study or the project at the time of interim analyses while the study is ongoing.

All unblinded personnel will otherwise keep randomization lists and data or information that could unblind other study team members confidential and secure except as described above.

Following final database lock all roles may be considered unblinded.

Table 6-4 Blinding and unblinding plan (up to Study Week 29)

Role	Time or Event			
	Randomi- zation list generated	Treatment allocation & dosing	Safety event (single subject unblinded)	Interim Analysis
Patients	B	B	UI	B
Site staff	B	B	UI	B
Unblinded site staff e.g., pharmacy staff	UI	UI	UI	UI
Drug Supply and Randomization Office	UI	UI	UI	UI
Unblinded sponsor staff e.g., for study treatment re-supply, unblinded monitor(s), sample analyst(s),	UI	UI	UI	UI
Statistician/statistical programmer/ data analysts CCI	B	B	UI	UI
All other sponsor staff not identified above (trial team, project team, management & decision boards, support functions)	B	B	UI	UI

UI: Allowed to be unblinded on individual subject level

B: Remains blinded

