4.4 Purpose and timing of interim analyses/design adaptations

A first interim analysis (IA1) is planned after approximately 50% of randomized patients have completed all Week 29 assessments. The efficacy endpoints up to Study Week 29 along with relevant safety data will be examined as a preliminary evaluation of therapeutic effects. A second IA (IA2) is planned after all enrolled patients have completed their Week 29 assessments.

An ongoing blinded review of safety data will be conducted at frequent intervals.

Additional interim analyses may be conducted to support decision making concerning the current clinical study or project, the sponsor's clinical development projects in general or in case of any safety concerns.

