6.5 Dose modification

Investigational study treatment dose adjustments and/or interruptions are not allowed and must be discussed with the sponsor on a case-by-case basis if considered appropriate by the investigator.

Study drug dose adjustments are not permitted in this study; in case of an AE or for any reason (e.g., non-compliance, operational issue) resulting in a deviation from the required dosing scheme, consultation and agreement with Novartis will be necessary to decide whether the patient can continue or needs to be withdrawn from the treatment.

If not avoidable, dosing can be brought forward or delayed by up to 1 week for administrative reasons. The subsequent dose should be given according to the original schedule (i.e., do not move subsequent dose dates).

Any change in dosing must be recorded on the Dosage Administration Record eCRF.

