12.8 Sample size calculation

12.8.1 Primary endpoint(s)

In total 120 patients are to be randomized to 4 treatment arms, aiming at 30 patients per treatment arm. The sample size may be re-estimated based on results of interim analysis 1 based on observed response rate in placebo arm.

With 30 patients in either active or the matching placebo arm, there is 84% chance that the predefined efficacy criteria ([Section 12.4.2](#)) will be met, assuming the true difference in proportion of responders is 25% in favor of active arm and placebo responder rate is 17% ([Furie et al 2017](#)). If the true difference from placebo is zero, the chance of meeting efficacy criteria is around 10%. The same assumption is made for either VAY736 or CFZ533 cohort.

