7.1.1 Variables

The primary endpoint is a composite of SRI-4 response at Week 29 with sustained reduction in oral corticosteroid from Week 17 through Week 29.

SRI-4 response is defined as below:

- having ≥ 4 points reduction from baseline in SLEDAI-2K score AND
- no new BILAG-2004 A organ domain score and no more than one new BILAG-2004 B organ domain scores compared with baseline AND
- < 0.3 mm or < 10 mm point increase if scaled 0 to 3 or 0 to 100 mm, respectively in the physician's global assessment from baseline

Sustained reduction in oral corticosteroids is defined as below:

- ≤ 5 mg/day or \leq baseline dose, whichever is lower, at Week 17
AND
- no increase of that dose from Week 17 through Week 29

When all these criteria are met, the patient is considered as a responder. However, patients receiving CS dosing in addition to the baseline CS dosing levels or subsequent, reduced levels attained at Week 17 after completing the guided corticosteroid tapering period will be considered non-responder for primary endpoint:

- if total daily CS dose is > 30 mg/d prednisone or equivalent, or
- increased daily CS dose is administered > 2 days within a 4-week treatment cycle, or
- daily CS dose is increased within 2 weeks of Study Visit Week 29.

Patients who have taken other rescue medication or prohibited medication (Table 6-3 of study protocol, e.g., new immune suppressive agents or biologics) or drop out before Week 29 will also be considered non-responder for the primary endpoint. Where acute CS administration occurs for purposes other than the treatment of SLE disease activity, patient responder status will be discussed on a case-by-case basis.

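### Individual treatment codes may reach the wider sponsor team at IA1 while responder status and primary-set membership are still open for about half the patients, with no visible rule that these be decided blind

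*Protocol*

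**What the plan says.** **Blinding.** Protocol 6.4 states that patients, site staff, assessors and the clinical trial team "will remain blind to the identity of the treatment from the time of randomization until end of the Week 29 visit". One of the rules listed under that sentence allows trial-team members to be unblinded at the interim analyses. The section then lets the study statistician share unblinded information with the clinical team: "unblinded summaries and unblinded individual data can be shared with the team for interim analyses". The team may in turn pass unblinded results to other sponsor staff for internal decisions.

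Table 6-4 covers the period up to Week 29. Its row "All other sponsor staff not identified above (trial team, project team, management & decision boards, support functions" changes from blinded at treatment allocation to UI at the interim analysis. The footnote reads "UI: Allowed to be unblinded on individual subject level". Patients and ordinary site staff stay blinded in that column.

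**Timing.** Protocol 4.4: "A first interim analysis (IA1) is planned after approximately 50% of randomized patients have completed all Week 29 assessments". Protocol 12.8.1: "In total 120 patients are to be randomized to 4 treatment arms, aiming at 30 patients per treatment arm".

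**Judgements that shape the primary result.**
- Protocol 6.2.4 and SAP 7.1.1: when acute corticosteroids are given for a reason other than SLE activity, "patient responder status will be discussed on a case-by-case basis". Neither place names who decides.
- Protocol 12.1 and SAP 4: the PD analysis set leaves out patients with deviations that bear on PD data. Protocol 12.4 and SAP 7.1 use this set for the primary analysis.

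**The concern.** Protocol 4.1 justifies blinded randomization as the route to an unbiased efficacy assessment in a disease with a high placebo response. That protection is weakened if people who know a patient's arm, and perhaps the emerging effect, can still settle whether that patient counts as a responder or belongs in the analysis set. The plan permits this overlap. Codes may go to the wider team at IA1 with no visible restriction to patients past Week 29, while the two judgements stay open for patients who have not got there. With about 30 patients per arm, a few classifications can move the result that guides the development decision.

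**Working it through.** **1. Patients short of Week 29 at IA1.** Inputs: 120 planned (Protocol 12.8.1) and about 50% completed (Protocol 4.4). 120 × (1 − 0.5) = about 60 patients, or 60 / 4 = about 15 per arm. This is a ceiling. It counts patients whose status could still be open, not patients who will need a discretionary decision, and some of them may not have been randomized yet.

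**2. Which judgements remain open, and how closely they touch the endpoint.**

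| Judgement | Place | Effect on the primary result | Decider stated? | Visible blinding rule? |
|---|---|---|---|---|
| Responder status after non-SLE corticosteroids | Protocol 6.2.4, SAP 7.1.1 | Direct | No | No |
| Deviation-based exclusion from the PD set | Protocol 12.1, SAP 4 | Direct | No | No |
| Continuing treatment after a dosing deviation or missed dose | Protocol 6.5, 9.1.1 | Indirect | Sponsor, with the investigator | No |

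The third row is not part of the point. Protocol 9.1.1 keeps patients who stop treatment in the study, so stopping is not in itself non-response.

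**3. The plan's own operating characteristics.** The efficacy criteria (Protocol 12.4.2, SAP 7.1.3) are P(difference > 0) > 90% and P(difference > 15%) > 50%. Protocol 12.8.1 gives an 84% chance of meeting them at 17% versus 42%, and around 10% with no difference. The prior is described only as weakly informative, so I assume independent Beta(1,1) priors without covariates. For x active and y placebo responders out of 30:

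- posterior active rate ~ Beta(1 + x, 31 − x); posterior placebo rate ~ Beta(1 + y, 31 − y);
- chance of go = Σ over all (x, y) meeting both criteria of Bin(x; 30, p_active) × Bin(y; 30, p_placebo).

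Results: 81.2% at 17% versus 42%, and 6.0% at 17% versus 17%. The stated pair is approached more closely by the first criterion alone (82.1% and 10.8% with Beta(0.5, 0.5) priors). Across the priors tried, power for both criteria runs from about 76% to 87%. Because the prior is not stated, this gap is not offered as an error, and the present point does not depend on it.

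**4. Where the decision changes.** With 5/30 placebo responders:

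| Active responders | P(diff > 0) | P(diff > 15%) | Both met? |
|---|---|---|---|
| 9/30 | 0.88 | 0.41 | No |
| 10/30 | 0.93 | 0.53 | Yes |

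Any rule on counts has such an edge, so this alone says little about risk.

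**5. Effect of directed reclassification on the false-go rate.** Replace x by x + k in the sum of step 3, with a true 17% in both arms:

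| Active non-responders counted as responders (k) | False-go rate |
|---|---|
| 0 | 6.0% |
| 1 | 11.3% |
| 2 | 19.3% |

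The k = 1 increase, 11.3 − 6.0 = 5.3 percentage points, is the chance under no difference that the result falls exactly one active responder short. Beta(0.5, 0.5) priors give the same three rates to one decimal place. Tighter logistic priors, N(0, 2.5²), start from a lower false-go rate of 3.0%, and at 5/30 placebo they move the threshold from 10 to 11 active responders.

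**The case against.** The other side has real weight.

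- **The blinding text is consistent.** A reader might take Protocol 6.4 to contradict itself. It does not: unblinding of the team at interim analyses is one of the rules attached to the sentence that keeps the team blind.
- **The design is disclosed and non-confirmatory.** It is labelled patient- and investigator-blind, and site assessments stay protected. Sponsor access at an interim is a defensible choice in an exploratory study. Barring every team member from all individual data would be a trade-off, not a correction.
- **Limits may exist out of sight.** Protocol 12.7 and SAP 3 are redacted, and the content of SAP Table 4-1, which links deviation codes to analysis sets, is not visible. One cannot say that no safeguard exists, nor that PD-set exclusions are free discretion.
- **Sponsor control of responder status is inferred.** The decider is not named, and the provision covers only acute corticosteroids for non-SLE purposes. The remaining corticosteroid rules are numerical.
- **The treatment-continuation route is weak.** Protocol 6.5 does say that "consultation and agreement with Novartis will be necessary to decide whether the patient can continue or needs to be withdrawn from the treatment", but such patients stay under follow-up.
- **The size is hypothetical.** Reclassification must occur, and in the decisive direction. The criteria are described as a guide to decisions.
- **Unblinding is permitted, not required.** Protocol 6.4 also asks unblinded staff to keep confidential anything that could unblind colleagues.

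What stands after this: the confidentiality duty exempts the sharing described earlier in the same section. The permission in 6.4 and Table 6-4 is broad as written. The two direct judgements carry no visible requirement to be made blind. If the redacted sections do contain a limit, 6.4 and Table 6-4 still need to be aligned with it.

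**Conclusion.** The point holds as a gap in sponsor-side safeguards. Individual codes may go to the trial team, project team and decision boards at IA1, when up to about 60 of the 120 planned patients have not completed Week 29. Case-by-case responder status and deviation-based exclusion from the primary set remain open for those patients without a visible blinding rule.

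The size is illustrative: a false-go rate of about 6% becomes about 11% with one reclassification in favour of active. This rests on Beta(1,1) priors, 30 per arm, no covariates, a true 17% in both arms and an assumed direction. The documents give no count of such decisions.

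A reader might infer that the trial is effectively unblinded for half its patients, or that codes have influenced classifications. The documents support neither. Patients and sites remain blinded, and nothing shows that codes were used in this way.

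**What to change.** 1. **SAP 7.1.1 and SAP 4.** Add: *Case-by-case responder decisions and deviations affecting the PD set are made and documented by personnel without access to treatment codes, before the codes for the patients concerned are released.* Name the deciding role.
2. **Protocol 6.4 and Table 6-4.** At IA1, limit individual-level codes released to the wider team to patients whose Week 29 data, responder status and PD-set status are final. Otherwise provide arm-level summaries. The statistician, programmers and data analysts who run IA1 keep the access they already have. The possible sample-size re-estimation in Protocol 12.8.1 uses the placebo response rate, which a summary supplies.
3. **If IA1 has passed.** This seems likely, because SAP 5 refers to an earlier interim report with final CFZ533 results and SAP 1.4 refers to the last 3 patients in follow-up. In that case, document and report who held codes when these two kinds of decision were made.

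The cost is a few sentences and a change to the table, with no additional analysis. The one drawback is that team members who make these decisions cannot see individual codes for a patient until that patient's status is final.

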6.5 Dose modification

Investigational study treatment dose adjustments and/or interruptions are not allowed and must be discussed with the sponsor on a case-by-case basis if considered appropriate by the investigator.

Study drug dose adjustments are not permitted in this study; in case of an AE or for any reason (e.g., non-compliance, operational issue) resulting in a deviation from the required dosing scheme, consultation and agreement with Novartis will be necessary to decide whether the patient can continue or needs to be withdrawn from the treatment.

If not avoidable, dosing can be brought forward or delayed by up to 1 week for administrative reasons. The subsequent dose should be given according to the original schedule (i.e., do not move subsequent dose dates).

Any change in dosing must be recorded on the Dosage Administration Record eCRF.

6.6 Additional treatment guidance

6.6.1 Treatment compliance

Study treatment will be administered at the clinical sites for all patients; therefore, treatment compliance is monitored by the clinical staff and recorded in the eCRF.

Serum/plasma concentrations for VAY736 and CFZ533 will be obtained, and pharmacokinetic parameters (measures of treatment exposure) will be determined in all patients treated with VAY736 and CFZ533, as detailed in [Section 8.5.1](#).

6.6.2 Recommended treatment of adverse events

Patients experiencing disease signs and symptoms may receive symptomatic care with over-the-counter, anti-inflammatory/analgesic agents such as NSAIDs and paracetamol.

For patients with SLE disease signs and symptoms not adequately controlled by symptomatic care and/or have more severe SLE disease manifestations not suitable for such treatment may receive rescue therapy with corticosteroids if determined by the PI to be medically necessary. However, any increases in corticosteroid dosing during the blinded treatment period to treat increased SLE disease activity may result in the patient labeled as a non-responder for primary endpoint (see [Table 6-2](#) and [Table 6-3](#) for allowed and prohibited concomitant medications, respectively).

Any medication used to treat AEs must be recorded on the Concomitant Medications/Significant non-drug therapies CRF.

6.6.3 Emergency breaking of assigned treatment code

Emergency code breaks must only be undertaken when it is required to in order to treat the subject safely. Most often, study treatment discontinuation and knowledge of the possible treatment assignments are sufficient to treat a study subject who presents with an emergency condition. Emergency treatment code breaks are performed using the IRT system. When the investigator contacts the system to break a treatment code for a subject, he/she must provide the requested subject identifying information and confirm the necessity to break the treatment code for the subject. The investigator will then receive details of the investigational drug treatment for the specified subject and a fax or email confirming this information. The system will automatically inform the Novartis monitor for the site and the study team that the code has been broken.

It is the investigator's responsibility to ensure that there is an appropriate procedure in place to allow access to the IRT system at any time in case of emergency.

In addition, oral and written information to the subject must be provided on how to contact his/her backup in cases of emergency, or when he/she is unavailable, to ensure that un-blinding can be performed at any time.

An assessment will be done by the appropriate site personnel and sponsor after an emergency unblinding to assess whether or not study treatment should be discontinued for a given patient. In case the study drug will be discontinued, patients should continue the study without receiving study treatment in order to monitor their safety, wherever possible.

6.7 Preparation and dispensation

Each study site will be supplied with study drug in packaging as described under investigational and control drugs section.

Preparation of both study drugs is described in detail in a separate Pharmacy Manual.

A unique medication number is printed on the study medication label.

Investigator staff will identify the study medication kits to dispense to the patient by contacting the IRT system and obtaining the medication number(s).

Each study site will be supplied with study drug in packaging as described in [Section 6.1](#).

An unblinded pharmacist at each site will identify the study medication kits to dispense to the patient by contacting the IRT system and obtaining the medication number(s) and will prepare the study medication accordingly. VAY736, CFZ533 and corresponding placebos will be administered to the patient via s.c. injection or i.v. infusion, respectively, at the study site by trained and competent site personnel. Please refer to the respective Pharmacy Manuals for further details.

7 Informed consent procedures

Eligible subjects may only be included in the study after providing (witnessed, where required by law or regulation), Institutional Review Board (IRB)/ Independent Ethics Committee (IEC)-approved informed consent.

Informed consent must be obtained before conducting any study-specific procedures (e.g., all of the procedures described in the protocol). The process of obtaining informed consent must be documented in the subject source documents.

Novartis will provide to investigators in a separate document a proposed model informed consent form (ICF) that complies with the ICH GCP guidelines and regulatory requirements and is considered appropriate for this study. Any changes to the proposed model consent form suggested by the investigator must be agreed by Novartis before submission to the IRB/IEC. The model ICFs will be adapted locally to comply with local regulations.

Information about common side effects already known about the investigational drug can be found in the IB. This information will be included in the subject informed consent and should be discussed with the patient before and during the study as needed. Any new information regarding the safety profile of the investigational drug identified between IB updates will be communicated as appropriate, for example, via an investigator notification or an aggregate safety finding. New information might require an update to the informed consent and then must be discussed with the patient.

Women of childbearing potential must be informed that taking the study treatment may involve unknown risks to the fetus if pregnancy were to occur during the study and agree that in order to participate in the study, they must adhere to the contraception requirements.

For patients receiving SoC background therapy, contraception requirements and pregnancy warnings must be discussed with the PI, as per local practices.

A copy of the approved version of all consent forms must be provided to Novartis/sponsor after IRB/IEC approval.

8 Visit schedule and assessments

The Assessment schedule lists all assessments and indicates with an “X” at which visits they are to be performed. All data obtained from these assessments must be entered into the eCRF and must be supported in the patient’s source documentation.

Patients should be seen for all visits/assessments as outlined in the assessment schedule or as close to the designated day/time as possible. Missed or rescheduled visits should not lead to automatic discontinuation. Patients who prematurely discontinue the study for any reason should be scheduled for a visit as soon as possible, at which time all of the assessments listed for the final visit will be performed. At this final visit, all dispensed investigational product should be reconciled, and the adverse event and concomitant medications recorded on the CRF. Patients who prematurely discontinue the treatment with study drug for any reason should be encouraged to continue their study participation and complete all safety study visits as deemed necessary by the investigator, if possible.

[figure not shown]
As per [Section 4.6](#), during a public health emergency as declared by local or regional authorities e.g., pandemic, epidemic or natural disaster that limits or prevents on-site study visits, alternative methods of providing continuing care may be implemented by the investigator as the situation dictates. If allowed by local Health Authority and depending on operational capabilities, phone calls and virtual contacts (e.g., tele consult) or visits by site staff/ home nursing staff to the participant’s home can replace on-site study visits for the duration of the disruption and until it is safe for the participant to visit the site again.

Table 8-1 Assessment Schedule, Cohort 1 & 2 – Treatment period

Epoch	Screening		Treatment																	EoT
Visit Name	Screen	Base-line ²	Treatment – blinded period										Treatment – open label period							EoT
Visit Numbers ¹	1	20	110	120	130	140	150	160	170	180	190	200	210	220	230	240	250	260	299	
Days	-28 ±2	-1 to 1	1	15 ±2	29 ±2	57 ±2	85 ±2	113 ±2	141 ±2	169 ±3	197 ±3	211 ±2	225 ±3	253 ±3	281 ±3	309 ±3	337 ±4	340 ±1	365 ±5	
Weeks	-4	-1 to 1	1	3	5	9	13	17	21	25	29	31	33	37	41	45	49	49	53	
Months	-1	-1 to 1	1	1	2	3	4	5	6	7	8	8	9	10	11	12	13	13	14	
Informed consent	X																			
CCI																				
In/Exclusion criteria	X	X																		
Medical history	X																			
Demography	X																			
Vital signs ³	X	X		X	X	X	X	X	X	X	X	X	X	X	X	X	X		X	
Physical Examination	X	X		X	X	X	X	X	X	X	X	X	X	X	X	X	X		X	
Electrocardiogram (ECG)	X	X			X		X		X		X			X		X			X	
Corticosteroid induction ⁴			X ⁴								X ⁴									
SLEDAI-2K	X	X			X	X	X	X	X	X	X		X	X	X	X	X		X	
BILAG-2004	X	X			X	X	X	X	X	X	X		X	X	X	X	X		X	
CCI																				
PhGA - VAS (physician)	X	X			X	X	X	X	X	X	X		X	X	X	X	X		X	
PGA – VAS (patient)	X	X			X	X	X	X	X	X	X		X	X	X	X	X		X	
Hepatitis & HIV Screen ⁷	X																			
CMV Monitoring ^{6,25}	X		X		X	X	X	X	X	X	X		X	X	X	X	X		X	

Epoch	Screening		Treatment																	EoT
Visit Name	Screen	Base-line 2	Treatment – blinded period										Treatment – open label period							EoT
Visit Numbers ¹	1	20	110	120	130	140	150	160	170	180	190	200	210	220	230	240	250	260	299	
Days	-28 ±2	-1 to 1	1	15 ±2	29 ±2	57 ±2	85 ±2	113 ±2	141 ±2	169 ±3	197 ±3	211 ±2	225 ±3	253 ±3	281 ±3	309 ±3	337 ±4	340 ±1	365 ±5	
Weeks	-4	-1 to 1	1	3	5	9	13	17	21	25	29	31	33	37	41	45	49	49	53	
Months	-1	-1 to 1	1	1	2	3	4	5	6	7	8	8	9	10	11	12	13	13	14	
HepB monitoring ^{7,24}					X	X	X	X	X	X	X		X	X	X	X	X		X	
Tuberculosis test ⁷	X																		X	
Pregnancy test ⁵	X	X		X	X	X	X	X	X	X	X	X	X	X	X	X	X		X	
Hematology ⁷	X	X		X	X	X	X	X	X	X	X	X	X	X	X	X	X		X	
Clinical Chemistry ⁷	X	X		X	X	X	X	X	X	X	X	X	X	X	X	X	X		X	
CCI																				
Coagulation Panel ⁷	X	X ⁶					X ⁶				X ⁶								X ⁶	
Autoantibodies ⁷	X	X					X				X				X				X	
CCI																				
IMI blood sample ^{7, 16}		X			X					X										
IMI urine sample ^{7, 16}		X			X					X										
CCI																				
Steroid taper ¹¹					X	X	X	X												
PK Cohort 1 ¹²			X	X	X	X	X	X	X	X	X	X	X	X	X	X	X	X	X	
PK Cohort 2 ¹²			X ¹³	X	X ¹³	X	X ¹³	X	X	X	X ¹³	X	X ¹³	X	X ¹³	X	X ¹³		X	
Immunogenicity ^{12, 14}		X		X			X				X	X			X				X	
CCI																				

Epoch	Screening		Treatment																EoT
Visit Name	Screen	Base-line ²	Treatment – blinded period								Treatment – open label period								EoT
Visit Numbers ¹	1	20	110	120	130	140	150	160	170	180	190	200	210	220	230	240	250	260	299
Days	-28 ±2	-1 to 1	1	15 ±2	29 ±2	57 ±2	85 ±2	113 ±2	141 ±2	169 ±3	197 ±3	211 ±2	225 ±3	253 ±3	281 ±3	309 ±3	337 ±4	340 ±1	365 ±5
Weeks	-4	-1 to 1	1	3	5	9	13	17	21	25	29	31	33	37	41	45	49	49	53
Months	-1	-1 to 1	1	1	2	3	4	5	6	7	8	8	9	10	11	12	13	13	14

IRT	X	X ²³		X	X	X	X	X	X	X	X	X	X	X	X	X	X		X
Dose administration ²¹			X ²²	X ⁶	X	X	X	X	X	X	X ²²	X ⁶	X	X	X	X	X		

Adverse Events	As required																		
Concomitant Treatment	As required																		
Comments	As required																		

^X Assessment to be recorded in the clinical database, EoT – End of Treatment

¹ Visit structure given for internal programming purpose only

² Baseline visit may be combined with Visit 110 at Day 1

³ Body Weight, Height (screening only), Temperature, Blood Pressure, Pulse Rate

⁴ Only for Cohort 1 (VAY736); i.v. CS to be applied approximately 1 hour before first dose

⁵ Pregnancy test on Visit 1 (Screening) in serum, all other visits in urine, only females

CCI

⁷ Central Lab

CCI

¹¹ Corticosteroids should be tapered down to 5 mg/day or lower

¹² Samples are collected pre-dose unless otherwise stated

¹³ Cohort 2 (CFZ533): take one PK sample at pre-dose and another sample 90 min AFTER THE START of i.v. infusion

¹⁴ Cohort 1 (VAY736): serum Cohort 2 (CFZ533): plasma

CCI

¹⁶ Only selected sites

CCI

²¹ Dosing must be done after all assessments are completed, except for PK blood sampling in Cohort 2 (CFZ533) at visits V110, 130, 150, 190, 210, 230 and 250 where pre and post dose blood sampling is required

²² Post-dose observation time of 2 hours after first dose for Cohort 1 (VAY736), only

²³ Randomization assignment at Baseline

²⁴ This test will only be applied as follows: for HepBc Ab positive patients at screening, followed by monthly HBV DNA and HBsAg testing

²⁵ CMV test (CMV serologies IgM and IgG and CMV DNA by PCR) will be performed in the local laboratory at screening for all patients. Starting from visit 110 this testing will be repeated on a monthly basis only for patients randomized to Cohort 2 (CFZ533).

Table 8-2 Assessment Schedule, Cohort 1 & 2 - Follow up period

Epoch	Follow Up - Cohort 1&2				Secondary Follow-Up					EoS Disposition
Visit Name	Follow Up			FU 1 Cohort 1/ EoS Cohort 2	FU 2 Cohort 1 ³					EoS Disposition ²
Visit Numbers ¹	300	310	320	399	400	410	420	430	440	1999
Days	393 ±5	421 ±5	449 ±5	477 ±5	645 ±10	813 ±10	981 ±10	1233 ±10	1569 ±10	-
Weeks	57	61	65	69	93	117	141	177	225	0
Months	15	16	17	18	24	30	36	45	57	0
Vital signs ⁴		X		X						X
Physical Examination		X		X						X
Electrocardiogram (ECG)		X		X						X
SLEDAI		X		X						X
BILAG-2004		X		X						X
CCI										
PhGA-VAS (physician)	X	X	X	X	X	X	X	X	X	X
PGA-VAS (patient)	X	X	X	X	X	X	X	X	X	X
HepB monitoring ^{7,15,16}	X	X	X	X	X	X	X	X	X	X
CMV monitoring ^{6, 17}	X	X	X	X						
Tuberculosis test				X						
Pregnancy test ⁵	X	X	X	X	X					X
Hematology ⁷	X	X	X	X	X	X	X	X	X	X
Clinical Chemistry ⁷	X	X	X	X	X	X	X	X	X	X
CCI										
Coagulation Panel ⁶		X ⁶		X ⁶						
Autoantibodies ⁷		X		X						X

Epoch	Follow Up - Cohort 1&2				Secondary Follow-Up					EoS Disposition
Visit Name	Follow Up			FU 1 Cohort 1/ EoS Cohort 2	FU 2 Cohort 1 ³					EoS Disposition ²
Visit Numbers ¹	300	310	320	399	400	410	420	430	440	1999
Days	393 ±5	421 ±5	449 ±5	477 ±5	645 ±10	813 ±10	981 ±10	1233 ±10	1569 ±10	-
Weeks	57	61	65	69	93	117	141	177	225	0
Months	15	16	17	18	24	30	36	45	57	0

CCI

PK Cohort 1	X	X	X	X						X
PK Cohort 2	X	X	X	X						
Immunogenicity		X		X						X

The CCI logo, consisting of the letters 'CCI' in a bold, red, sans-serif font.

Adverse Events	As required
Concomitant Treatment	As required
Comments	As required

^x Assessment to be recorded in the clinical database, EoS – End of Study

¹ Visit structure given for internal programming purpose only

² Cohort 1 (VAY736), only: End of study visit will be performed as soon as practically possible but no more than approximately 4 weeks after this clinical protocol amendment is approved, independently of B cell recovery criteria reached as long as visit occurs 2 years after EoT. If a patient's B cell recovery is confirmed at Week 69, no additional follow-up or EoS visit is needed, and therefore Week 69, FU 1 Cohort 1/ EoS Cohort 2 will be the last visit.

³ Cohort 1 (VAY736), only: Follow-up visits in Cohort 1 have to be performed up to 2 years after EoT or until B cell count is at ≥ 50 cells/ul or at least 80% of baseline levels, whichever occurs earlier. If a patient B cells recovery is confirmed at Week 69 no additional follow-up or EOS visit is needed, and therefore Week 69, FU 1 Cohort 1/ EoS Cohort 2 will be the last visit.

⁴ Body Weight, Temperature, Blood Pressure, Pulse Rate

⁵ Pregnancy test on Visit 1 (Screening) in serum, all other visits in urine, only women

CCI

⁷ Central Lab

CCI

¹⁵ Monthly HepB monitoring will be continued after V399 to V400 for all patients in Cohort 1 who tested positive for HepB core Ab. For patients who do not achieve B cell recovery, testing will continue at every visit until EoS visit Cohort 1.

¹⁶ This test will only be applied for HepBc Ab positive patients at screening; followed by monthly HBV DNA and HBsAg testing.

¹⁷ CMV test (CMV serologies IgG and IgM and CMV DNA by PCR) will be continued at the local laboratory after V300 to V399 on a monthly basis only for patients randomized to Cohort 2 (CFZ533)

